8.1 Patient

8.1.1 Standard of Care and Investigational Treatment

	Pre-Treatment (within 28 days of treatment start)*	During each treatment course					4-6 weeks after 2 nd treatment course	Follow-up at Day 90, 180, 270, 360	
		Day 1 ¹	Day 5	Day 15 or 17	During IL-2 administration (Day 17-22)	Day 24, 31, 38, 45			
EVALUATIONS									
Written consent	X								
Medical history	X								
Disease Characteristics	X								
Pathology review of outside dx	X								
Transfusion History	X						X		
Concomitant meds	X	X					X		
Physical exam	X	X	X ⁶	X ⁶	X ⁶	X ⁶	X		
Vital signs	X	X		X					
Weight	X	X		X	3 x a week during IL-2	X			
Height	X								
ECOG Performance Status	X	X					X		
Survival Status								X ⁷	
LABORATORY									
CBC w/ diff ²	X	X	X	X	daily during IL-2	X	X		
Na, K, Cl, CO ₂ , BUN, creatinine, uric acid, phos, LDH, Mg	X	X	X	X		X			
ALT/AST, bili, total protein, albumin, alk phos	X	X		X		X			
Chest X-ray	X								
INR/PTT	X								
Pregnancy test ³	X								
HLA typing (low resolution)*	X								
Recipient Viral Serology	X								
ECHO/MUGA*	X								
Bone Marrow Bx/Asp ⁴	X ⁴					X ⁵	X ⁴		
Investigational TREATMENT									
Decitabine IV		Day 1-5							
Vorinostat PO			Day 6-15						
NK cell infusion (research)				Day 17					
IL-2 tiw for 3 doses (research)					X (start Day 17)				

* CBC, dff, CMP, chemistries within 14 days of study treatment start, HLA typing may be done at any time

- 1- Course 1 Day 1 evaluations need not be repeated if pre-study evaluations were done within 14 days of 1st treatment
- 2- CBC with diff weekly throughout all treatment with increased frequency as clinically indicated
- 3- Women of childbearing potential only; serum or urine
- 4- Bone marrow aspirate and biopsy with standard flow cytometry, conventional cytogenetics, and MDS/AML FISH panel will be conducted at study initiation and at the completion of the 2nd cycle for standard disease assessment or at time of study withdrawal if early termination.
- 5- Prior to course 2 ONLY in patients who enrolled in this study as a prior treatment failure per section 4.2.2 or any patient who is discontinuing study treatment after 1 course
- 6- Clinical assessments will occur at a minimum of weekly up until the NK cell infusion on Day +17 after which clinical assessments will occur daily until the day after the final IL-2 administration.
- 7- By record review, patient contact, etc.

8.1.2 Patient – Research Related

	Before start of each chemo course	Before NK cell infusion	After each treatment course			
		Day 17	Day 24	Day 31	Day 38	Day 45 ³
Adverse Event Monitoring	Per section 11					
Chimerism – PB (unseparated)*	x		x	x ¹	x ¹	x ¹
60 ml of heparinized blood (green top tubes)*	x	x	x	x	x	x
10 ml of serum (red top tube)* for HAMA ²		x (post infusion)				
10 ml of serum (red top tube)*	x	x	x	x	x	x
BM 30 ml (heparinized)*	At the time of each bone marrow biopsy for clinical reasons					

1 – continue chimerism monitoring until they disappear

2 –draw sample in the event of a grade 4 infusion related toxicity occurs – refer to section 8.1.3

3 – the day 1 treatment course 2 sample may be eliminated if the patient is ready to start course 2 at day 45

*For the Cancer Center’s Translational Therapy Lab (TTL) – refer to section 8.3 for shipping instructions. (U of MN chimerism samples to be sent directly to the Molecular Diagnostics)

As recognized with novel therapies, as in this study, the timing of protocol directed research samples may miss important patient specific events. For this reason, up to 3 extra samples for a total of 180 ml of blood may be drawn at additional time points that are not specified above.

8.1.3 Assessment for HAMA in the Event of a Grade 4 Infusion Reaction

If a patient experiences a CTCAE v 4 grade 4 infusion related reaction (life-threatening consequences; urgent intervention indicated) serum will be drawn and be tested for the presence of HAMA. If HAMA is detected, the results will be reported to the FDA in an expedited manner per section 11.4. If not, it will be noted at the time of the IND annual report.

8.2 Donor – Research Related

	Screen	Day 15
Consent	X	
HLA Typing (class 1) SOC - not research	X	
Type and Screen (ABO/RH /Indirect Antiglobulin)	X	X
Donor Infectious Disease Panel	X	X ¹
EBV IgG	X	
BMT/DNA marker	X	
Medical History	X	
Physical Exam	X	X
CBC, diff, platelet	X	X
ALT, creatinine	X	
Pregnancy test, if applicable	X	
60 ml of heparinized blood (green top tubes)*		X
10 ml of serum (red top tube)*		X
Leukapheresis		X

1 - repeat if more than 7 days since baseline testing

*For the Cancer Center's Translational Therapy Lab (TTL) – refer to section 8.3 for shipping instructions.

8.3 Sample Shipping Information

Samples are shipped the day of collection to the Masonic Cancer Center's Translational Therapy Lab (TTL) for overnight delivery in an insulated container with a frozen gel pack Monday-Thursday. Refer to the Affiliate Laboratory Manual for additional details.

Translational Therapy Core Facility
University Of Minnesota
[name]
[name]
[name]
[contact]
[contact]

9.0 Study Endpoints

This study is designed as a two stage study of the combination of Decitabine and Vorinostat and haploidentical NK cell infusion. The primary endpoint is clinical response (CR + PR + HI) at the end of the required 2 cycles of therapy. An assessment of response differences between untreated/minimally treated and those with prior treatment failures will be conducted.

The secondary endpoints include evaluation of safety tolerability, the proportion of patients who become transfusion independent, the association of the in vivo NK cell expansion with clinical response, and 1 year Overall Survival.

Clinical responses are defined in Appendix VI.

Determination of toxicities will be important for this new combination. As per NCI CTCAE Version 4.0, the term toxicity is defined as adverse events that are classified as either possibly, probably, or definitely related to study treatment. The maximum grade for each type of toxicity will be recorded for each patient, and frequency tables will be reviewed to determine toxicity patterns. In addition, we will review all adverse event data that is graded as 3, 4, or 5 and classified as either “unrelated or unlikely to be related” to study treatment in the event of an actual relationship developing.

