2	10/03/12	In response to IRB ancillary committee review: Revise donor eligibility to adults only (18 – 75 years of age) In response to study initiation meeting: Synopsis, Sections 7.3 and 10.3: Clarify that the NK cell product will be divided in half prior to IL-2 activation and that the IDS will prepare the IL-2 used in the overnight incubation for all patients (U of MN and Mayo Clinic), for course #2 product MCT will send a post-thaw and post IL-2 cell sample to TTL; Sections 13.2 and 11.3: Revise early study stopping rule to include any non-hematologic, non-infectious grade 4-5 event, regardless of attribution and recalculate patient number thresholds; Section 4.11 (new) and Checklist: Exclude patient who have received 7+3 or other AML-type induction chemotherapy; Section 11.2: adjust post-IL-2 targeted toxicity assessments to coincide with clinic visits; Other minor clarifications and corrections throughout	Yes
3	01/04/13	Sections 7.3 and 7.4: update lot release information in that the final product must contain at least 20% NK cells (previously at least 30%) as permitted by the FDA and to match the current CMC; additional edits – Section 7.5 re-write IL-2 dose modification guidelines for clarity; Section 8.1.1: clarify follow-up for survival only for the purpose of calendar creation (at Day 90, 180, 270, 360), Section 8.2: delete donor repeat type and screen at day 15; other minor edits	no
4	06/17/13	Section 7.3 and 7.4: change the %NK cells required for lot release to 30% reversing the January 2013 change to 20%; clarify course #2 cell preparation procedures	no

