11.3 Required Reporting: Mayo Clinic to the Masonic Cancer Center

Serious events: Beginning with the first dose of decitabine and continue through day 45 of the last treatment course, as an affiliate, Mayo will report all events meeting the definition of serious, regardless of attribution or expectedness, within 24 hours of knowledge of the event. After day 45 of the last treatment course, the investigator must report upon knowledge any event that is serious, unexpected and felt to be at least possibly related to study therapy.

Reports are to be submitted to the Study Coordinator at the University of Minnesota Masonic Cancer Center (MCC) using the SAE reporting form found in OnCore. The MCC Study Coordinator will facilitate reporting to the University Of Minnesota IRB and the FDA as required.

Stopping rule events: Any grade 4 or 5 non-hematologic, non-infectious toxicity occurring through day 45 of the last treatment course will count toward the early study stopping rule per section 13 and must be reported to the MCC Study Coordinator using the Early Stopping Rule Report Form found OnCore under the reports tab.

No more than one excess toxicity event will be accumulated per patient within in the same episode of toxicity (i.e. a grade 4 event worsening to a grade 5 is a single event) or when multiple events occur concurrently.

Events that count toward an early stopping rule do not necessarily constitute a serious adverse event requiring expedited reporting and

should be reported as such only if they meet the criteria for expedited reporting as defined in section 11.1.

Lot release issues: Any safety issues associated with the final lot release at the treating institution must be reported immediately to either [name] or [name] at the University of Minnesota (contact information on page 2) with follow-up reporting to MCC Study Coordinator using the Deviation Report found in OnCore.

Affiliate institutions will be responsible for submitting reportable events to their institutional IRB and any other required local regulatory entities.

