13.2 Early Stopping Rule for Toxicities

The complications and adverse events will be closely monitored in this study. The hypothesized rate of having grade 4 or 5 non-hematologic, non-infectious toxicities for the approach is 5%. Enrollment will be stopped and the trial re-evaluated if the grade 4 or 5 toxicity rate shows signs to exceed 15%. This means enrollment will be stopped and the study re-evaluated if there are 3 patients with a non-hematologic, non-infectious grade 4-5 toxic event occurring through day 45 of the last treatment course out of the first 7 patients, 4 out of 18, 5 out of 29, 6 out of 40, and 7 patients at any time. Toxicities such as infections, including but not limited to pneumonia, bacteremia, cellulitis, and neutropenic fever, etc are known results of high risk MDS and will not be included as toxicities attributed to the study therapy. Assessment for toxicities will begin upon initiation of trial therapy and will conclude 2 weeks after last dose of study related treatment. These stopping rules of a statistical sequential probability ratio test designed for no more than 5% the probability of type I error and at least 80% statistical power.

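### The toxicity stopping rule does not say whether a grade 4-5 event must be judged related to treatment in order to count

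*Combined protocol and SAP*

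**What the plan says.** Section 9.0 gives the word *toxicity* a meaning tied to attribution: "the term toxicity is defined as adverse events that are classified as either possibly, probably, or definitely related to study treatment". It adds that grade 3 to 5 events called unrelated or unlikely will also be reviewed.

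The stopping rule appears in two places, and neither mentions attribution:

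- Section 11.3: "Any grade 4 or 5 non-hematologic, non-infectious toxicity occurring through day 45 of the last treatment course" counts toward the rule.
- Section 13.2: enrollment stops at set numbers of patients with a "non-hematologic, non-infectious grade 4-5 toxic event occurring through day 45 of the last treatment course".

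Other text bears on how to read these:

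- In Section 11.3, the serious-event paragraph directly above the stopping-rule paragraph requires the affiliate site to report "regardless of attribution or expectedness, within 24 hours of knowledge of the event". The stopping-rule paragraph has no such phrase.
- Section 13.2 says that infections "will not be included as toxicities attributed to the study therapy".
- The table in Section 11.2 requires every grade 4 and 5 event to be documented, including those called unrelated or unlikely.
- The revision 2 entry in the revision log reads: "Revise early study stopping rule to include any non-hematologic, non-infectious grade 4-5 event, regardless of attribution and recalculate patient number thresholds".

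**The concern.** A coordinator deciding whether to file a stopping-rule report for a grade 4 cardiac event judged unlikely to be related finds no answer in the current text. If the Section 9.0 definition applies, the event does not count. If *any* in 11.3 means what it says on its face, it does.

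The trial runs at two sites. The paragraph containing *any* sits in the section on Mayo Clinic's reporting. Section 11.4, which covers the coordinating center, refers to Section 13 for the rule, and Section 13.2 contains the wording about attributed toxicities. Staff at the two sites could apply different counts in good faith.

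This is an open, single-arm study of a new multi-agent combination in sick patients, where attribution of a single event is a soft judgement. If it filters the count, the rule reacts to a lower rate than the rate at which events occur. If it does not, the rule also reacts to background events. The 5% and 15% rates mean different things in the two cases, and Section 13.2 does not say which is meant.

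**Working it through.** **Inputs from Section 13.2.** Acceptable rate p0 = 0.05, unacceptable rate p1 = 0.15, type I error 0.05, power 0.80 (so β = 0.20), sequential probability ratio test. Thresholds: 3 of the first 7, 4 of 18, 5 of 29, 6 of 40, 7 at any time. **From Section 13.1.** At most 51 patients enrolled, 46 evaluable; all treated patients enter the toxicity evaluation, so 51 is the main case.

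**Reproducing the thresholds.** The test stops at k events among n patients when

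k·ln[p1(1−p0)/(p0(1−p1))] − n·ln[(1−p0)/(1−p1)] ≥ ln[(1−β)/α].

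The three logarithms are 1.2098, 0.1112 and ln 16 = 2.7726. Dividing by the first, stop when k ≥ 2.292 + 0.0919·n. The largest n for each k is:

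| k | 3 | 4 | 5 | 6 | 7 |
|---|---|---|---|---|---|
| n | 7.7 | 18.6 | 29.5 | 40.3 | 51.2 |

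Rounded down, these are 7, 18, 29, 40 and 51, which are the plan's thresholds.

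**Operating characteristics.** An exact binomial recursion on the printed boundary, checked after every patient, gives a probability of stopping of 0.031 at a counted rate of 5% and 0.714 at 15% with 51 patients (0.028 and 0.649 with 46). That 0.714 is below the stated 80% is a separate matter; 0.714 is the reference value here.

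**Effect of attribution.** Let f be the share of qualifying events judged at least possibly related. The documents give no value, so f is an assumption and a range is shown. Under a related-only count, the rule sees a rate of f × 15%.

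| f (assumed) | Counted rate | P(stop), 51 patients | P(stop), 46 patients |
|---|---|---|---|
| 1.0 (all count) | 15.0% | 0.714 | 0.649 |
| 0.9 | 13.5% | 0.607 | 0.543 |
| 0.8 | 12.0% | 0.485 | 0.427 |
| 0.7 | 10.5% | 0.357 | 0.310 |
| 0.5 | 7.5% | 0.133 | 0.115 |

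With 51 patients, the share of the reference probability that is kept is 0.607/0.714 = 85%, 0.485/0.714 = 68%, 0.357/0.714 = 50% and 0.133/0.714 = 19%.

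**The opposite direction.** Suppose the rate of related events is the acceptable 5% and all events count. If unrelated events add 2 points (an assumption), P(stop) with 51 patients rises from 0.031 to 0.106; if they add 5 points, it rises to 0.315.

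**The case against.** The best case for leaving the text alone has three parts.

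1. **Intent is on record.** The revision 2 entry says that attribution is to be ignored and that thresholds were recalculated with that change. The later log entries list no change to the stopping rule, and *any* in 11.3 fits that intent. This stands as evidence of what was meant, and it makes the all-events reading the likelier one. A log entry is not operative text, however, and someone working from Sections 9.0, 11.3 and 13.2 would not find the instruction.

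2. **Section 9.0 may not govern the whole protocol.** Its sentence introduces the toxicity frequency tables. Sections 7.6, 7.10 and 11.2 add their own relatedness qualifier to *toxicity*, which would be redundant if the word already carried one. This has force. Against it, the sentence is worded as a definition of the term, and the infection sentence in 13.2 treats counted toxicities as attributed.

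3. **Oversight sees the events anyway.** Section 11.2 documents all grade 4-5 events, Section 9.0 reviews those called unrelated, the affiliate site reports serious events within 24 hours whatever their cause, and the monitoring council receives quarterly reports. So it would be wrong to infer that an event called unlikely disappears from view. But none of these steps puts it into the stopping count.

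Two stronger readings are tempting. One is that Sections 9.0 and 11.3 flatly contradict each other. They do not: *any toxicity* can be read within the Section 9.0 definition, and no current sentence says that only related events count. The other is that attribution would strip the rule of most of its ability to detect an excess. That holds only toward the low end of the assumed range. Because *possibly* related already meets the Section 9.0 definition, shares near 1 are plausible; at 90% the probability of stopping is still 0.61.

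**Conclusion.** The point stands as an ambiguity in a safety-critical definition. The plan does not state whether a qualifying grade 4-5 event must be attributed to treatment to count toward stopping, and current passages point in different directions.

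The possible loss runs from modest to large: from 0.71 to 0.61 if 90% of events are judged related, and to 0.13 if 50% are. These figures assume a true any-cause rate of 15%, 51 patients, independent events and a constant related share. They illustrate the sensitivity and do not predict what the trial would see.

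The boundary itself is not in error. It reproduces from the stated inputs, and its properties at 5% and 15% are the same for whichever event is counted. What is unsettled is which event that is.

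**What to change.** - In Sections 11.3 and 13.2, replace *toxicity* and *toxic event* in the stopping rule with *adverse event, regardless of attribution*. Keep the existing grade, non-hematologic and non-infectious limits and add no new exclusion. In particular, an exclusion for disease progression is not in either section; it would narrow a safety rule and bring back the causal judgement that the change removes.
- In Section 13.2, reword the infection sentence so that infections are excluded by type, without reference to attribution.
- State in Section 9.0 that its definition of *toxicity* does not govern the stopping rule.
- State in Section 13.2 that 5% and 15% are any-attribution rates, after the sponsor confirms that they were chosen on that basis.

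The cost is a short amendment to three sections. No new data are needed, because Section 11.2 already requires every grade 4-5 event, and the change matches the recorded intent. The downside is a somewhat higher chance of a pause for review if unrelated events are common: 0.106 or 0.315 instead of 0.031 in the two assumed background cases worked above.

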11.2 Adverse Event Documentation

Adverse events occurring after the initiation of any study treatment must be documented. Adverse events attributed to a study-related procedure which occur prior to the initiation of study treatment must be documented as well. Refer to appendix VII for a list of expected toxicities.

For the purposes of this study, adverse event documentation requirements will be determined based on grade, expectedness and relationship to study therapy as follows:

	Grade 1	Grade 2		Grade 3		Grade 4 and 5
	Expected or Unexpected	Expected	Unexpected	Expected	Unexpected	Expected or Unexpected
Unrelated Unlikely	Not required	Not required	Not required	Not required	Required	Required
Possible Probable Definite	Not required	Not required	Required	Required non-hematological	Required	Required
				Not required - hematologic events		

All patients will be monitored from the initiation of any study treatment through day 45 after the last dose of study treatment or the start of a new treatment, whichever occurs earlier, as it is expected that most treatment related adverse events will occur during this period. However, the investigator is obligated, upon knowledge of, to report any adverse event considered to be related to study treatment meeting the expedited reporting criteria in section 11.4.

In addition, adverse event collection will include targeted adverse events and unexpected adverse events at specific time points in relation to the NK cell infusion and post NK cell infusion IL-2 injections.

Targeted adverse events (Appendix IX) and unexpected events will be collected at the following time points. Adjust the day to match the time point description. All time points are 24 hours +/- 2 hours.

- Post-Chemo/Pre-NK cell infusion (day 17)
- A single assessment 1-2 hours post NK cell infusion/pre IL-2 injection (day 17)
- pre IL-2 dose 2
- pre IL-2 dose 3
- 48 hours post IL-2 dose 3 (or to coincide with day 24 clinic visit)
- 1 week after last IL-2 dose (or to coincide with day 31 clinic visit)

At each time point, the worst grade of the targeted toxicity since the last assessment or the previous 24 hours (whichever is shorter) will be recorded in addition to any unexpected toxicities felt at least possibly related to the NK cells and/or the IL-2.

In addition, although not always a reportable event, deaths will be recorded in OnCore upon knowledge in the follow-up tab.

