
 • flu-like syndrome (may include fever, chills, tiredness, headache, muscle and joint pain) • low blood pressure • nausea/vomiting • diarrhea • feeling weak • confusion • shortness of breath • flushing of the face • rash or dry, itchy skin • low urine output • abnormal blood tests which suggest that the drug is affecting the liver or kidneys 	
 • feeling dizzy • feeling drowsy • sores in the mouth or on the lips • loss of appetite • abdominal pain • increased heart rate or change in heart rhythm • swelling in the face, hands, or feet • trouble sleeping • trouble concentrating • runny nose • low platelet count with increased risk of bleeding* • low red blood cell count (anemia) with symptoms like tiredness, weakness, shortness of breath • low white blood cell count with increased risk of infection 	
 • allergic reaction* • cough • confusion • psychosis (loss of touch with reality) • depression • seizures • coma • damage to bowel, ruptured or bleeding bowel • serious infection • kidney failure • heart attack • stroke • breathing problems • death from low blood pressure, capillary leak syndrome, heart problems, or other complications

Refer to section 7.8 for NK cell expected toxicity

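### Section 9 promises a review of all unrelated grade 3-5 events and a maximum grade for every toxicity, but the section 11.2 table does not require all the events these need

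*Combined protocol and SAP*

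**What the plan says.** Section 9.0 makes two commitments about safety data.

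- **Maximum-grade tables.** "The maximum grade for each type of toxicity will be recorded for each patient, and frequency tables will be reviewed to determine toxicity patterns". Toxicity is defined there by attribution only: "the term toxicity is defined as adverse events that are classified as either possibly, probably, or definitely related to study treatment". No grade floor and no restriction by expectedness is given.
- **Attribution review.** "we will review all adverse event data that is graded as 3, 4, or 5 and classified as either" unrelated or unlikely to be related, in case a relationship later emerges.

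Section 11.2 then decides what has to be written down: "adverse event documentation requirements will be determined based on grade, expectedness and relationship to study therapy". Its table marks several combinations as not required. One cell is split, so that related expected grade 3 events are required if non-hematologic but "Not required - hematologic events". The same section sends staff to Appendix VII for the list of expected toxicities.

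Section 11.1 defines expectedness separately. An event is unexpected if it is not listed, or not listed at the observed specificity or severity. Events arising from the disease process or an underlying medical condition also count as unexpected.

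Safety and tolerability is the first secondary objective (section 1.2), and section 13.3 plans a toxicity rate with a 95% confidence interval.

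**The concern.** A table or review can be no more complete than the data collected for it. This is a single-arm trial of a new combination, so the safety description rests on these tables and on a second look at events that investigators called unrelated. That second look is most useful for an event already known to occur with one of the agents but blamed on something else. At grade 3, this is the kind of event that 11.2 leaves optional. If one site records optional events and the other does not, the pooled frequencies mix two collection rules.

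**Working it through.** No figure in the plan bears on this, so the check compares what section 9 needs with what section 11.2 requires, cell by cell, and then looks for another route that fills the gaps. The unrelated/unlikely row has six entries under six column heads, so the reading does not depend on a broken table.

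| Grade and expectedness | Unrelated/unlikely | Possible/probable/definite |
|---|---|---|
| 1 | not required | not required |
| 2 expected | not required | not required |
| 2 unexpected | not required | required |
| 3 expected, non-hematologic | not required | required |
| 3 expected, hematologic | not required | not required |
| 3 unexpected | required | required |
| 4 and 5 | required | required |

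(In the unrelated/unlikely row, grade 3 expected is a single cell in the protocol. It is split here only to align the rows.)

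**Attribution review.** It needs the grade 3-5 cells of the unrelated/unlikely row: grade 3 expected, grade 3 unexpected, and grade 4-5. That is 3 cells, of which 1 (grade 3 expected) is not required.

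**Maximum-grade tables.** They need the whole related row, which has 7 cells. Three are not required: grade 1, grade 2 expected, and grade 3 expected hematologic. The unrelated row does not enter, because section 9 defines toxicity as related events.

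**Other routes.**

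- *Appendix IX targeted form.* It has 14 named items plus an open row. Nausea, vomiting, diarrhea, fatigue and anorexia are not among the named items, although section 2.1.2 gives the first three and fatigue as typical dose-limiting effects of this drug class. For entries beyond the named items, 11.2 asks only for unexpected toxicities at least possibly related to NK cells or IL-2. There are six assessments per course, each looking back at most 24 hours, so the form covers at most 6 × 24 = 144 hours, or 6 days. Courses start 6 to 8 weeks (42 to 56 days) apart. The first assessment is on day 17, so days 1-15 are essentially uncovered.
- *Vorinostat log (section 7.2, Appendix VIII).* It takes free-text side effects for the ten vorinostat days, without grade or attribution.
- *Serious-event reporting.* Section 11.3 asks for all serious events regardless of attribution, but as a duty of Mayo to the coordinating center. The criteria in 11.4 are narrower.
- *Blood counts (section 8.1.1).* They are weekly throughout treatment and daily during IL-2, so cytopenias can be graded from laboratory data.

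**Which events the first gap reaches.** Under 11.1, a grade 3 event attributed to MDS or an underlying condition is unexpected, and so required. What clearly remains is a listed event attributed to something else, for example a grade 3 renal event blamed on a concomitant antimicrobial. The boundary is blurred because Appendix VII, to which 11.2 points, is broad and carries no grades. It lists serious infections, seizures and kidney failure, and even "death from low blood pressure, capillary leak syndrome, heart problems, or other complications". A reader who uses that list alone would call an infection attributed to MDS expected; a reader who uses 11.1 would call it unexpected. The two give opposite documentation rules for the same grade 3 event.

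**The case against.** The case on the other side is substantial, and most of it stands.

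- *Not required is not forbidden.* Sites may record these events, and the electronic case report forms and their embedded instructions (sections 12.1 and 12.2) are not in the documents. A reader might infer that every expected grade 3 event called unrelated is lost. The documents support only incomplete and possibly uneven capture.
- *Events blamed on MDS.* A reader might infer that a grade 3 seizure attributed to MDS escapes documentation. Under 11.1 it is unexpected and so required; only the Appendix VII pointer leaves doubt. Creatinine is also a targeted item and is on the scheduled chemistry panels.
- *Blank tables.* A reader might infer that patients whose worst related event was grade 1, 2 or 3 would be shown as free of toxicity. For grade 3 this does not hold: all related non-hematologic grade 3 events are required, and the hematologic ones can be recovered from the blood counts. Section 7.8.4 also says that prolonged anemia or thrombocytopenia will not count towards toxicity.
- *Deliberate choice.* Not requiring grade 1 and expected grade 2 events is a defensible limit on data burden, and section 9 could be read as tabulating whatever is collected. The choice can stand, but then section 9 should say so, because its wording promises more.

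The answer to the first two points does not remove the mismatch. The review is stated to cover all such events, and one of its cells is optional.

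**Conclusion.** Sections 9 and 11.2 cannot both be carried out as written. The attribution review can miss listed grade 3 events blamed on causes other than MDS or an underlying condition. The maximum-grade tables can understate low-grade toxicity outside the targeted list, chiefly nausea, diarrhea and fatigue. In cells, the gap is 1 of 3 for the review and 3 of 7 for the tables, and the hematologic one of those three is recoverable from the blood counts. The number of events cannot be derived, because the documents give no rates by grade.

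The conclusion assumes that the case report forms follow the 11.2 table. If they already ask for these events, the gap is one of wording only.

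It would be tempting to read this as a weakness in safety monitoring as a whole. The documents do not support that. Grade 4-5 events are required whatever their attribution, the stopping rule in section 13.2 uses only grade 4-5 events, and no decision rule of the trial changes. What is affected is the completeness and labelling of the descriptive safety results.

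**What to change.** 1. In the 11.2 table, change unrelated/unlikely, grade 3 expected, to required, and state that this applies at both sites. The section 9 review can then be done as promised.
2. Reconcile the definition of expectedness in 11.1 with the Appendix VII pointer in 11.2, and state which governs documentation. This still matters after step 1, because expectedness also decides whether related grade 2 events are recorded.
3. In section 9, restrict the maximum-grade tables to the grade and type cells that 11.2 collects, and say so in the table titles. Grade cytopenias from the scheduled blood counts and label them as laboratory-graded.

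The cost is modest extra data entry for grade 3 events and a narrower safety table, with no added visits or tests. A worst-grade entry per course for every common toxicity in Appendix VII would restore the wider table. However, the common columns hold 10 + 10 + 11 = 31 entries before overlaps are removed, or 62 per patient over two courses. That burden is debatable and is not needed to bring the two sections into line.
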